APPENDIX H. IMPACT OF WEIGHT ON QUALITY OF LIFE - LITE

Impact of Weight on Quality of Life Questionnaire—Lite Version (IWQOL-Lite)

Please answer the following statements by circling the number that best applies to you in the past week. Be as open as possible. There are no right or wrong answers.

Physical Function		ALWAYS TRUE	USUALLY TRUE	SOMETIMES TRUE	RARELY TRUE	NEVER TRUE
1.	Because of my weight I have trouble picking up objects.	5	4	3	2	1
2.	Because of my weight I have trouble tying my shoes.	5	4	3	2	1
3.	Because of my weight I have difficulty getting up from chairs.	5	4	3	2	1
4.	Because of my weight I have trouble using stairs.	5	4	3	2	1
5.	Because of my weight I have difficulty putting on or taking off my clothing.	5	4	3	2	1
6.	Because of my weight I have trouble with mobility.	5	4	3	2	1
7.	Because of my weight I have trouble crossing my legs.	5	4	3	2	1
8.	I feel short of breath with only mild exertion.	5	4	3	2	1
9.	I am troubled by painful or stiff joints.	5	4	3	2	1
10.	My ankles and lower legs are swollen at the end of the day.	5	4	3	2	1
11.	I am worried about my health.	5	4	3	2	1
Sel	f-esteem	ALWAYS TRUE	USUALLY TRUE	SOMETIMES TRUE	RARELY TRUE	NEVER TRUE
1.	Because of my weight I am self-conscious.	5	4	3	2	1
2.	Because of my weight my self-esteem is not what it could be.	5	4	3	2	1
3.	Because of my weight I feel unsure of myself.	5	4	3	2	1
4.	Because of my weight I don't like myself.	5	4	3	2	1
5.	Because of my weight I am afraid of being rejected.	5	4	3	2	1
6.	Because of my weight I avoid looking in mirrors or seeing myself in photographs.	5	4	3	2	1
7.	Because of my weight I am embarrassed to be seen in public places.	5	4	3	2	1

Se	xual Life	ALWAYS TRUE	USUALLY TRUE	SOMETIMES TRUE	RARELY TRUE	NEVER TRUE
1.	Because of my weight I do not enjoy sexual activity.	5	4	3	2	1
2.	Because of my weight I have little or no sexual desire.	5	4	3	2	1
3.	Because of my weight I have difficulty with sexual performance.	5	4	3	2	1
4.	Because of my weight I avoid sexual encounters whenever possible.	5	4	3	2	1
	•		•			

Pu	blic Distress	ALWAYS	USUALLY	SOMETIMES	RARELY	NEVER
-		TRUE	TRUE	TRUE	TRUE	TRUE
1.	Because of my weight I experience ridicule, teasing, or unwanted attention.	5	4	3	2	1
2.	Because of my weight I worry about fitting into seats in public places (e.g. theaters, restaurants, cars, or airplanes).	5	4	3	2	1
3.	Because of my weight I worry about fitting through aisles or turnstiles.	5	4	3	2	1
4.	Because of my weight I worry about finding chairs that are strong enough to hold my weight.	5	4	3	2	1
5.	Because of my weight I experience discrimination by others.	5	4	3	2	1
Wo	ork (Note: For homemakers and retirees, answer with respect to your daily activities.)	ALWAYS TRUE	USUALLY TRUE	SOMETIMES TRUE	RARELY TRUE	NEVER TRUE
1.	Because of my weight I have trouble getting things accomplished or meeting my responsibilities.	5	4	3	2	1
2.	Because of my weight I am less productive than I could be.	5	4	3	2	1
3.	Because of my weight I don't receive appropriate raises, promotions or recognition at work.	5	4	3	2	1
4.	Because of my weight I am afraid to go on job interviews.	5	4	3	2	1

APPENDIX I. EUROQOL-5D

Health Questionnaire

.

English version for the USA

USA (English) $\textcircled{$\otimes$}$ 2009 EuroQol Group EQ-5D ${}^{\rm M}$ is a trade mark of the EuroQol Group Page~90~of~92

Under each heading, please check the ONE box that best describes your health TODAY.

 \Box

 \square

 \Box

 \square

 \Box

MOBILITY

I have no problems walking I have slight problems walking I have moderate problems walking I have severe problems walking I am unable to walk

SELF-CARE

I have no problems washing or dressing myself
I have slight problems washing or dressing myself
I have moderate problems washing or dressing myself
I have severe problems washing or dressing myself
I am unable to wash or dress myself

USUAL ACTIVITIES (e.g. work, study, housework, family or

leisure activities)
I have no problems doing my usual activities
I have slight problems doing my usual activities
I have moderate problems doing my usual activities
I have severe problems doing my usual activities
I am unable to do my usual activities

PAIN / DISCOMFORT

I have no pain or discomfort I have slight pain or discomfort I have moderate pain or discomfort I have severe pain or discomfort I have extreme pain or discomfort

ANXIETY / DEPRESSION

I am not anxious or depressed
I am slightly anxious or depressed
I am moderately anxious or depressed
I am severely anxious or depressed
I am extremely anxious or depressed

	The best hea you can imagi	
• We would like to know how good or bad your health is TODAY.		100
• This scale is numbered from 0 to 100.		95
• 100 means the best health you can imagine.	 	90
0 means the worst health you can imagine.	+	85
• Mark an X on the scale to indicate how your health is TODAY.		80
 Now, please write the number you marked on the scale in the box below. 		75
		70
	± ±	65
	 	60
		55
YOUR HEALTH TODAY =		50
	+ +	45
		40
	#	35
		30
		25
		20
	 	15
		10
	±	5
	 	0
	The worst hea you can imag

1. INTRODUCTION

This statistical analysis plan (SAP) describes the statistical methods to be used for analyses and presentation of safety and efficacy data for the study ALK3831-A306. This document has been prepared based on Alkermes [ALK3831-A306](#) Study Protocol Amendment 2.0 (dated 25 Apr 2017)¹.

1.1. Study Objectives

1.1.1. Primary objective

The primary objective of this study is to evaluate the long term safety and tolerability of ALKS 3831 in subjects with schizophrenia.

1.2 Summary of the Study Design

Subjects that have completed the 4-week Treatment Period of the antecedent study, ALK3831-A305, within the past 7 days are eligible to be enrolled in the study. Subjects completing the 4-week Treatment Period of the antecedent study, ALK3831-A305, as inpatients may continue as inpatients for up to 1 week in this extension study. These subjects may be discharged from the inpatient unit at any time during this week based on Investigator's judgment.

Subjects enrolled in the study will be started on ALKS 3831 10/10 (10 mg olanzapine/10 mg samidorphan). The ALKS 3831 dose may be increased to 15/10 (15 mg olanzapine/10 mg samidorphan) or 20/10 (20 mg olanzapine/10 mg samidorphan) during the first week of treatment or thereafter, based on Investigator discretion. For subjects entering this study as outpatients, study staff will check in with them by phone on Day 3 to assess tolerability and determine if a dose increase to ALKS 3831 15/10 or 20/10 is needed. An Unscheduled Visit will be arranged mid-Week 1 for subjects requiring a dose increase. Following a dose increase, the dose may be decreased back to 15/10 or 10/10 if there are tolerability issues. Thus, dosing is flexible and subjects will receive ALKS 3831 10/10, 15/10, or 20/10 throughout the duration of the study, based on Investigator discretion. Dose adjustments can only be performed on-site at the study center. Subjects requiring dose adjustments between scheduled visits should arrange an Unscheduled Visit for the following procedures: study drug return, adherence review, and study drug dispensation.

Safety assessments will include AE monitoring, clinical laboratory testing, vital signs, weight and waist circumference assessments, 12-lead ECGs, movement disorder assessments, including the Abnormal Involuntary Movement Scale (AIMS), Barnes Akathisia Rating Scale (BARS), Simpson Angus Scale (SAS), and the Columbia-Suicide Severity Rating Scale (C-SSRS).

[figure not shown]
Efficacy assessments to evaluate the durability of treatment effect will include Positive and Negative Syndrome Scale (PANSS) and Clinical Global Impressions-Severity (CGI-S).

Additional assessments include Impact of Weight on Quality of Life–Lite Questionnaire (IWQOL-Lite), Cigarette Use, and EuroQOL-5D (EQ-5D).

Subjects completing 52 weeks of treatment with study drug will be eligible to continue in the open-label, long-term safety study (ALK3831-A308) and will continue to receive ALKS 3831. Subjects not continuing in the ALK3831-A308 long-term safety study will enter a 4-week Safety Follow-up Period.

A schematic of the study design is provided in Figure 1.

Figure 1: Study Design Schematic

*Visits will occur weekly for the first 2 weeks, then biweekly thereafter. Outpatient subjects will be contacted by phone on Day 3 to determine if a dose increase is needed, and, if so, an unscheduled visit will be arranged mid-Week 1. The dose may be adjusted to either 10/10, 15/10, or 20/10 mg throughout the study period, based on Investigator discretion, and such dose adjustments will require subjects to visit the study site

2. SAMPLE SIZE CONSIDERATION

No formal sample size calculation is performed for this extension study. A sample size of approximately 390 is based on the estimated maximum number of subjects who might be expected to continue from the ALK3831-A305 study.

3. DATA ANALYSIS

3.1. General Statistical Methodology

Baseline for efficacy or safety analysis is defined as the last non-missing assessment before the first dose of ALKS 3831 in ALK3831-A306 study, and it will be used for all efficacy and safety analysis unless specified otherwise.

Antecedent study baseline, defined as the last non-missing assessment on or before the first dose of study drug during double-blind treatment period in ALK3831-A305 study, may be explored as applicable.

Treatment sequence is defined according to the treatment assignment in antecedent and current studies as ALKS 3831/ALKS 3831 (ALKS 3831 in both ALK3831-A305 study and ALK3831-A306 study), OLZ/ALKS 3831 (olanzapine in ALK3831-A305 study and ALKS 3831 in ALK3831-A306 study), or PBO/ALKS 3831 (placebo in ALK3831-A305 study and ALKS 3831 in ALK3831-A306 study).

In general, descriptive statistics: n, mean (\pm standard deviation [SD]), median, minimum, and maximum, for continuous variables and number and percentage of subjects in each category for categorical variables will be provided.

All statistical tests and confidence intervals (CIs), unless stated otherwise, will be 2-sided and will be set at an alpha level of 0.05.

All source data will be presented as subject data listings.

3.2. Definitions of Analysis Populations

3.2.1. Safety Population

The Safety Population will include all subjects who enrolled and received at least 1 dose of study drug during the treatment period. The Safety Population will be used for the safety analyses.

3.2.2. Efficacy Population

The Full Analysis Set (FAS) will include all subjects in the Safety Population who have at least one postbaseline PANSS assessment.

3.3. Disposition

The number and percentage of subjects completing or prematurely discontinuing the study including reasons for discontinuation will be summarized by treatment sequence and overall for the following:

- Subjects who enrolled in the study
- Subjects in the Safety Population
- Subjects in the FAS Population

- Subjects who completed the treatment period
- Subjects who discontinued treatment along with reasons for discontinuation

3.4. Protocol Deviation

Subjects with major protocol deviations in the following categories will be summarized by treatment sequence and overall. A supportive listing will be provided as well.

- Did not meet the inclusion/exclusion criteria
- Received prohibited medications
- Lack of adherence with study medication, as defined by subjects taking less than 70% of protocol specified amount of study medication
- Dosing error

3.5. Demographics and Baseline Characteristics

Demographics and baseline characteristics such as gender, age, race, ethnicity, weight, and BMI will be summarized by treatment sequence and overall for the Safety and FAS population.

3.6. Prior and Concomitant Medication

Prior medications are defined as medications taken prior to the first dose of study drug in ALK3831-A306 study. Concomitant medications are defined as medications taken on or after the first dose of study drug in ALK3831-A306 study. All medications will be coded using the World Health Organization WHO-DD Enhanced + Herbal (version: March 2016) or higher.

Concomitant medications are defined as medications taken during the treatment period and will be summarized by the preferred drug name for the Safety population. All reported medications (including those initiated after the last dose of study medication) will be included in listing. For the summary table, if a subject has taken a concomitant medication more than once, the subject will be counted only once for that medication.

3.7. Treatment Adherence Rate and Duration of Study Drug Administration

3.7.1. Treatment Adherence Rate

Treatment adherence to the daily dosing schedule during treatment period will be summarized by treatment sequence for Safety Population. Treatment adherence will be calculated as follows:

$$100 \times \frac{\text{Total tablets dispensed} - \text{total tablets returned} - \text{total tablets lost}}{\text{Total tablets scheduled to be taken}}$$

3.7.2. Duration of Study Drug Administration

Duration of study drug administration (ALKS 3831) is defined as the number of days from the date of the first dose of study drug to the date of the last dose of study drug, inclusive (ie, last dose date – first dose date + 1 day). Duration of study drug administration will be summarized for the Safety Population by treatment sequence and overall.

The overall mean and modal dose of olanzapine will be summarized by treatment sequence and overall. Number and percentage of subjects will be summarized by their final dose level by treatment sequence and overall.

3.8. Efficacy Analyses

3.8.1. General Considerations

All statistical analysis will be performed at the 5% significance level. All confidence intervals (CI) will be 2-sided 95% confidence intervals. Efficacy analysis will be carried out using the FAS population. PANSS total and subscale scores, CGI-S, PANSS response analyses and body weight will be based on both observed data and the LOCF (last observation carried forward) imputation, that is, the last observed non-missing postbaseline value will be carried forward for missing postbaseline assessments.

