3.8.2. Efficacy Analysis

The following endpoints will be used to evaluate durability of treatment effect and summarized by treatment sequence and overall for FAS population:

- Change from baseline in PANSS total score, and subscale scores (positive, negative, and general psychopathology subscales) by visit
- Change from baseline in PANSS Excited Component (EC) score (comprised of 5 items, P4. excitement, G4. tension, P7. hostility, G8. uncooperativeness, and G14. poor impulse control) by visit
- Change from baseline in PANSS Marder factor scores by visit
- Change from baseline in CGI-S by visit
- Proportion of Subjects with PANSS response ($\geq 30\%$ improvement from baseline in PANSS total score)
- Time to first relapse
- Time to first remission
- Time to discontinuation

In general, continuous and categorical endpoints will be summarized using descriptive statistics by treatment sequence and overall. Change from baseline within the treatment sequence and overall may also be tested using an one-sample t-test.

The PANSS Marder factor model² consisted of the following 5 factors:

- Negative symptoms
 - N1. blunted affect
 - N2. emotional withdrawal
 - N3. poor rapport
 - N4. passive social withdrawal
 - N6. lack of spontaneity
 - G7. motor retardation
 - G16. active social avoidance
- Positive symptoms
 - P1. delusions
 - P3. hallucinatory behavior
 - P5. grandiosity
 - P6. suspiciousness
 - N7. stereotyped thinking
 - G1. somatic concern
 - G9. unusual thought content
 - G12. lack of judgment and insight
- Disorganized thought
 - P2. conceptual disorganization
 - N5. difficulty in abstract thinking
 - G5. mannerisms and posturing
 - G10. disorientation
 - G11. poor attention
 - G13. disturbance of volition
 - G15. preoccupation
- Uncontrolled hostility/excitement
 - P4. excitement
 - P7. hostility

- G8. uncooperativeness
- G14. poor impulse control
- Anxiety/depression
 - G2. anxiety
 - G3. guilt
 - G4. tension
 - G6. depression

Stabilization is defined as meeting all of the following stabilization criteria:

- PANSS total score ≤ 80
- PANSS score ≤ 4 on each of the following items:
 - P2: conceptual disorganization
 - P3: hallucinatory behavior
 - P6: suspiciousness
 - G9: unusual thought content

After a subject achieves stabilization, relapse and remission are defined as following:

- Relapse: $\geq 30\%$ increase in PANSS total score or re-hospitalization for psychotic symptoms.

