3.9.3.2. Weight and Body Mass Index

Weight (kg), BMI (kg/m^2) and waist circumferences (cm) (baseline and change from baseline) will be summarized using both observed data and LOCF imputation for missing data. Absolute

and percent change from baseline in body weight will be summarized by treatment sequence and overall.

Number and percentage of subjects with $\geq 7\%$ or $\geq 10\%$ weight gain from baseline based on the observed data and LOCF will be summarized by treatment sequence and overall and by visit.

Subgroup analysis by region (US vs non-US) will be performed.

In addition, number and percentage of subjects with weight change values considered as PCS occurring at any post-baseline visit will be summarized by treatment sequence and overall. Criteria for PCS are presented below. The percentages will be calculated relative to the number of subjects in the Safety Population with at least one post-baseline value. A supportive listing will be provided for subjects with PCS values.

Table 6: Criteria for Potentially Clinically Significant (PCS) Changes from Baseline in Body Weight

Parameter	Criteria
Body Weight	Decrease from Baseline $\geq 7\%$ Increase from Baseline $\geq 7\%$

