7. GENERAL STATISTICAL METHODOLOGY

In general, summary statistics (n, mean, SD, median, minimum, and maximum for continuous variables, and number and percentage of subjects in each category for categorical variables) will be provided by treatment sequence. All summary tables will be based on observed data, and missing values will not be imputed, unless otherwise indicated. Measurements collected from unscheduled visits or repeated assessments will not be included in the by-visit summary tables or figures, but will be included in the analyses for the PCS postbaseline values, and subject listings. Source data for the summary tables will be presented as subject data listings.

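### Missing 52-week weight, BMI, waist and PANSS data are handled only by observed cases and LOCF; the two need not bracket the truth, and no missing-at-random analysis is planned

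*SAP*

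**What the plan says.** SAP 3.8.1 covers PANSS total and subscale scores, CGI-S, PANSS response and body weight: "PANSS response analyses and body weight will be based on both observed data and the LOCF (last observation carried forward) imputation". It defines LOCF so that "the last observed non-missing postbaseline value will be carried forward for missing postbaseline assessments".

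SAP 3.9.3.2 applies the same pair to weight, BMI and waist circumference, which "will be summarized using both observed data and LOCF imputation for missing data". It does so again for the proportions with ≥7% or ≥10% "weight gain from baseline based on the observed data and LOCF will be summarized by treatment sequence and overall and by visit". BMI and waist rest on this section, not on 3.8.1.

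The SAP's default in Section 7 is observed data: "All summary tables will be based on observed data, and missing values will not be imputed, unless otherwise indicated". The two sections above are exceptions to it. Neither says whether the observed-case or the LOCF table is the main one.

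The analysis is otherwise descriptive. SAP 3.8.2 adds only that "Change from baseline within the treatment sequence and overall may also be tested using an one-sample t-test". No likelihood-based model, multiple imputation or sensitivity analysis for missing data appears in the SAP. The protocol does not mention LOCF.

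**The concern.** The only objective is long-term safety and tolerability. Protocol 5.3 gives the reason for the study: earlier treatment periods stop at 24 weeks and this one runs to 52. The product is meant to limit olanzapine weight gain (Protocol 5.1), so the Week 52 weight result is one of the main things a reader will take from the study.

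For each drop-out, LOCF fills Week 52 with a value taken at or before exit. That amounts to assuming that weight would not have changed afterwards. Observed cases use only the subjects who stayed, and describe all enrolled subjects only if leaving is unrelated to the outcome.

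Two passages make that hard to presume. Protocol 7.3 requires discontinuation at HbA1c ≥6.5%, a metabolic outcome that may travel with weight gain. Protocol 5.1 reports that discontinuation on olanzapine has been linked to weight gain and metabolic effects. If heavier gainers leave, both planned summaries can be low together, and showing them side by side gives false reassurance.

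**Working it through.** **Inputs from the documents.** Follow-up is 52 weeks and about 390 subjects are planned. Weight is measured after baseline at Weeks 1, 2, 4, 6, 8 and then every 4 weeks from 12 to 52, which is 16 visits (Protocol Table 3). Drop-outs are not replaced (7.4) and are asked to attend an early-termination visit close to the last dose (7.3). There is no planned figure to reproduce: no drop-out rate, SD or weight course on ALKS 3831 is given. The one long-term weight figure, 9.4 kg over up to 18 months, is for olanzapine alone. Everything below rests on assumptions.

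**Step 1: LOCF when drop-out is unrelated to gain.** Assume a constant hazard with total drop-out d, so λ = −ln(1−d)/52, and a mean course g(t) with g(52) = 4 kg. Then

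LOCF mean = ∫ f(t) g(t) dt + (1−d) g(52), where f is the drop-out density on 0-52 weeks.

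- Linear gain: LOCF/true = d / (−ln(1−d)).
- Plateau with a 20-week time constant: LOCF/true = [0.05/(λ+0.05)] × [1−(1−d)e^(−2.6)] / [1−e^(−2.6)], with e^(−2.6) = 0.0743.

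| d | Linear ratio | Linear LOCF | Plateau ratio | Plateau LOCF |
|---|---|---|---|---|
| 30% | 0.3/0.3567 = 0.841 | 3.36 kg | 0.8794 × 0.9480/0.9257 = 0.901 | 3.60 kg |
| 40% | 0.4/0.5108 = 0.783 | 3.13 kg | 0.8358 × 0.9554/0.9257 = 0.863 | 3.45 kg |
| 50% | 0.5/0.6931 = 0.721 | 2.89 kg | 0.7895 × 0.9629/0.9257 = 0.821 | 3.28 kg |

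LOCF is 16-28% low for linear gain and 10-18% low for the plateau. In this scenario the observed-case mean is unbiased at 4 kg, and that table is already planned.

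**Step 2: drop-out that depends on gain.** Simulation with n = 390, 120 replicates and the protocol's weight visits. For the linear and plateau courses the assumed true Week 52 gain is 6.0 kg; individual slopes have SD 5 kg at Week 52 and the residual SD is 1.2 kg. ML is maximum likelihood with unstructured mean and covariance, which is what an MMRM gives. Under MAR, each kg of observed gain above average multiplies the drop-out hazard by e^0.25 ≈ 1.28. Under MNAR, the hazard depends on the unobserved individual slope. The three figures in each cell are for increasing drop-out.

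| Course and mechanism | Realised drop-out | Observed cases (kg) | LOCF (kg) | ML (kg) |
|---|---|---|---|---|
| Linear, MCAR | 20/35/50% | 5.97/5.98/5.93 | 5.25/4.67/4.04 | 5.97/5.97/5.96 |
| Linear, MAR | 24/40/55% | 5.29/4.69/4.09 | 5.09/4.38/3.70 | 6.03/6.01/6.03 |
| Linear, MNAR | 16/26/35% | 5.11/4.56/4.01 | 4.88/4.18/3.56 | 5.63/5.30/5.01 |
| 8-week plateau, MAR | 24/40/55% | 5.24/4.68/4.10 | 5.55/5.21/4.85 | 6.00/6.01/5.98 |

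Under gain-dependent drop-out both planned summaries fall below 6.0 kg in every row. Which of the two is worse depends on the course.

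**Step 3: direction.** If mean gain peaks at Week 12 and falls to a true 3.0 kg, LOCF under MCAR gives 3.21/3.26/3.36 kg, which is too high. If mean change is zero and drop-out is MCAR, LOCF is unbiased.

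**Step 4: limits of the model.** ML recovers the true mean under MCAR and MAR only. Under MNAR it cuts the bias for the linear course but not always: for the peak-and-fall course it gives 2.63/2.28/1.99 kg, against 2.59/2.32/2.15 for LOCF and a true value of about 3.0.

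**The case against.** The strongest reply is that this is an open-label, single-treatment, descriptive study with no formal sample size and no between-group comparison; its only test is an optional one-sample t-test. Observed data are planned next to LOCF. SAP 3.9.3.2 also has a table that needs no carry-forward, in which the "number and percentage of subjects with weight change values considered as PCS occurring at any post-baseline visit will be summarized", with ≥7% gain among its criteria. The Kaplan-Meier analysis of discontinuation will show how much is missing.

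Most of this is accurate, and it limits the weight of the point. It does not remove it. The observed-case table is safe only if leaving is unrelated to gain. The any-visit table does not estimate status at Week 52 and misses gain after exit.

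A second reply is that an MMRM on on-treatment data estimates change as if everyone had stayed on drug, including subjects who must stop under the HbA1c rule, and that this target is debatable for a safety study. That is a fair point. It calls for the target to be stated and for the planned tables to be kept. An unstructured covariance over 16 weight visits also has 16 × 17/2 = 136 parameters, so a fallback structure is needed.

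A reader might go further and infer three things that the documents do not support:

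- That LOCF necessarily understates weight gain in the product's favour. This needs weight to keep rising. No course on ALKS 3831 is given, baseline follows a 4-week antecedent study, and one treatment sequence switches from olanzapine, so a plateau or a fall is possible.
- That LOCF biases PANSS in a known direction. It can hide later improvement or later worsening.
- That a mixed model avoids the bias. It does so only under missing at random.

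**Conclusion.** The point holds as a gap in the analysis plan that is cheap to close. It is not an error that invalidates the study. The two planned summaries rest on assumptions that Protocol 5.1 and 7.3 give reason to doubt, and they can err in the same direction.

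The size cannot be derived from the documents. The 10-28% shortfall in Step 1 illustrates LOCF alone, in a scenario where the observed-case table is right. The scenario that matters more is gain-dependent drop-out. In the linear MAR example, at 40% realised drop-out, LOCF gives 4.38 kg and observed cases 4.69 kg against a true 6.0 kg. Both illustrations depend on assumed drop-out, variability and weight course. The direction for weight is conditional on that course; for PANSS it is open.

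**What to change.** - **Main by-visit estimate of mean change** in weight, BMI, waist, PANSS and CGI-S: an MMRM on observed on-treatment data with visit, treatment sequence, visit-by-sequence and baseline value. Use an unstructured covariance with a prespecified fallback if it does not converge. State that it targets change as if subjects stayed on treatment and that it assumes missing at random.
- **Week 52 proportions** (≥7% and ≥10% weight gain, PANSS response): multiple imputation from a matching model, since an MMRM for means does not give them.
- **Sensitivity analysis:** delta-adjusted imputation, shifting the imputed values of drop-outs over a stated range, to cover missing not at random.
- **Keep** the observed-case and LOCF tables as supportive.
- **Settle one detail at the same time:** Protocol Table 3 puts Week 52, early termination and end of treatment in one column, and SAP 6.1 uses the nominal eCRF visits. State how early-termination values are mapped, so that they do not enter the observed Week 52 summary.

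The cost is modest programming on data already collected, with no change to study conduct. The downside is reliance on a missing-at-random assumption, which the SAP must state and the sensitivity analysis must probe.
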